## **DOSAGE AND ADMINISTRATION**

### **1. Abortion and Indications 1-4**

An initial dose of 1 mL of HEMABATE Sterile Solution (containing the equivalent of 250 micrograms of carboprost) is to be administered deep in the muscle with a tuberculin syringe. Subsequent doses of 250 micrograms should be administered at 1½ to 3½ hour intervals depending on uterine response.

An optional test dose of 100 micrograms (0.4 mL) may be administered initially. The dose may be increased to 500 micrograms (2 mL) if uterine contractility is judged to be inadequate after several doses of 250 micrograms (1 mL).

The total dose administered of carboprost tromethamine should not exceed 12 milligrams and continuous administration of the drug for more than two days is not recommended.

## **2. For Refractory Postpartum Uterine Bleeding:**

An initial dose of 250 micrograms of HEMABATE Sterile Solution (1 mL of HEMABATE) is to be given deep, intramuscularly. In clinical trials it was found that the majority of successful cases (73%) responded to single injections. In some selected cases, however, multiple dosing at intervals of 15 to 90 minutes was carried out with successful outcome. The need for additional injections and the interval at which these should be given can be determined only by the attending physicians as dictated by the course of clinical events. The total dose of HEMABATE should not exceed 2 milligrams (8 doses).

*Parenteral drug products should be inspected visually for particulate matter and discoloration prior to administration, whenever solution and container permit.*

## **HOW SUPPLIED**

HEMABATE Sterile Solution is available in the following packages:

1 mL ampoules	NDC 0009085605
10 x 1 mL ampoules	NDC 0009085608

Each mL of HEMABATE contains carboprost tromethamine equivalent to 250 mcg of carboprost.

HEMABATE must be refrigerated at 2° to 8° C (36° to 46° F).

Duff, Sanders, and Gibbs; The course of labor in term patients with chorioamnionitis; *Am. J. Obstet. Gynecol.*; vol. 147, no. 4, October 15, 1983 pp 391-395.

This product's label may have been updated. For current full prescribing information, please visit [www.pfizer.com](http://www.pfizer.com)

**Rx only**

*Distributed by*  
 **Pharmacia & Upjohn Co**  
Division of Pfizer Inc, NY, NY 10017

LAB00325.0  
Revised December 2013

**PARTNERS HUMAN RESEARCH COMMITTEE  
PROTOCOL SUMMARY**

**Answer all questions accurately and completely in order to provide the PHRC with the relevant information to assess the risk-benefit ratio for the study. Do not leave sections blank.**

**PROTOCOL TITLE**

Second-line Uterotonics in Postpartum Hemorrhage: A Randomized Clinical Trial

**FUNDING**

n.a.

**VERSION DATE**

04/19/2022

**SPECIFIC AIMS**

Concisely state the objectives of the study and the hypothesis being tested.

The purpose of this study is to prospectively compare the efficacy of the two most commonly used second-line uterotonic agents in postpartum hemorrhage (PPH): methylergonovine maleate (methylergonovine) and 15-methyl prostaglandin F2a (carboprost). Study participants with abnormal bleeding immediately post Cesarean delivery will receive, upon request, methergine and/or carboprost in a randomized fashion after oxytocin. The choice of carboprost or methylergonovine as the first additional uterotonic to be administered will be randomized and all members of the care team will be blinded to the randomization. Dosing and timing of the uterotonic will be unaltered from standard of care. Uterine tone score, blood loss, need for additional uterotonic, need for transfusion and interventions to control bleeding will be recorded. We hypothesize that patients receiving methylergonovine will have a 1-point greater reduction in uterine tone (on a 0-10 scale) at 10 minutes after administration compared to carboprost.

**BACKGROUND AND SIGNIFICANCE**

Provide a brief paragraph summarizing prior experience important for understanding the proposed study and procedures.

Primary PPH is defined by the American College of Obstetricians and Gynecologists as a cumulative blood loss >1000 mL or blood loss

accompanied by signs of hypovolemia within 24 hours of delivery. It remains the leading source of maternal morbidity and mortality worldwide with uterine atony identified as the underlying cause in up to 80% of cases [Combs et al. *Obstet Gynecol* 1991;77:69–76. Dildy GA. *Clin Obstet Gynecol.* 2002; 45(2): 330-44]. Oxytocin is routinely administered prophylactically during the third stage of labor to decrease the risk of PPH [Westhoff et al. *Cochrane Database Syst Rev* 2013; 10:CD001808], and it is considered the first-line medical treatment for PPH. When postpartum bleeding persists, a multidisciplinary approach combining mechanical, pharmacologic, and surgical measures is indicated. The most effective second-line uterotonic agent remains unknown and a lack of consensus exists regarding the best pharmacologic management of PPH.

Recent literature indicates that methylergonovine may be superior to carboprost in the treatment of PPH [Butwick et al. *AJOG* 2015], but due to the unpredictable and emergent nature of PPH, high quality evidence of their comparative efficacy is scarce. This study will be the first to prospectively compare the two agents in a randomized fashion thereby allowing for direct comparison of their efficacy.

## **RESEARCH DESIGN AND METHODS**

Briefly describe study design and anticipated enrollment, i.e., number of subjects to be enrolled by researchers study-wide and by Partners researchers. Provide a brief summary of the eligibility criteria (for example, age range, gender, medical condition). Include any local site restrictions, for example, “Enrollment at Partners will be limited to adults although the sponsor’s protocol is open to both children and adults.”

The study will be conducted as a randomized, double blinded prospective trial. All patients of participating obstetricians will initially be given a standard information packet from their obstetrician’s office at their 28-week visit. The packet will contain basic information regarding their delivery as well as a copy of the study Consent Form and a Flier outlining this study’s goals and methods. Patients meeting eligibility criteria who plan vaginal or cesarean delivery and have reach 37 weeks gestation or greater, will be asked by their obstetrician for permission to be contacted by a study co-investigator by email. Those patients who are willing to be contacted will be sent an email reminding them of the study with a copy of the Study Flier and Consent Form attached to the email.

Eligibility criteria will include all female patients ages 18-50 with delivery of a viable fetus (24 weeks gestation or above) by non-emergent cesarean section (C/S) who experience abnormal immediate postpartum bleeding.

Exclusion criteria for enrollment in the study will include non-English speaking patients requiring an interpreter who are undergoing urgent, non-

scheduled C/S, patients with pre-existing systemic hypertension (HTN) or any hypertensive disorder of pregnancy, patients with cardiovascular disease, patients with asthma, patients who refuse to accept blood transfusion (e.g. Jehovah's Witnesses), patients with a known coagulopathy or abnormal baseline coagulation profile, patients with known or suspected hypersensitivity to either of the two study drugs, and patients with known or suspected delayed PPH after leaving the operating room from the cesarean delivery.

We anticipate enrolling 1250 patients in order to randomizing a total of 100 patients for this study, based on a calculation for 80% power to detect a mean difference of uterine tone score as small as 1.2 using a two-tailed two-sample t test, assuming a standard deviation of 1.9 and significant level at 0.05.

Patients will be recruited from those who deliver by cesarean section at the Brigham and Women's Hospital.

Briefly describe study procedures. Include any local site restrictions, for example, "Subjects enrolled at Partners will not participate in the pharmacokinetic portion of the study." Describe study endpoints.

Parturients will be assessed for eligibility using a pre-screening questionnaire at the time of admission to the Labor and Delivery (L&D) unit. Eligible patients will be given the opportunity to consent to participate in the study at the time of admission to the labor and delivery unit, or at the time of consent for elective cesarean section. Emergent cesarean section deliveries will be excluded.

Participants will receive standard care in terms of all medical and surgical interventions to manage postpartum bleeding. This will include a standard infusion of oxytocin immediately postpartum. If a second-line uterotonic is requested after oxytocin, the patient will be randomized by the anesthesiologist to either the "methylergonovine" or "carboprost" study group using a computer-generated randomization scheme printed on a piece of paper (called the Randomization sheet) in a sealed envelope. The anesthesiologist will document the patient MRN and study ID number on this Randomization Sheet and then return it to the envelope. The envelope will also contain a Uterine Tone Score Intraop Data Collection Sheet for documentation of the primary outcome as well as additional information, as described below.

Participants will receive either methylergonovine or carboprost depending on their randomization. The anesthesiologist will withdraw the appointed

medication (based on subject randomization) from the O.R. omnicell and administer it without revealing to anyone in the O.R. which drug was given. They will document the medication in the subject's Epic record in the usual fashion. Obstetricians and nursing staff are not able to view the Epic anesthesia record in real time, and therefore will not be able to see which medication was given by the anesthesiologist. Every effort will be made to avoid having the physician co-investigator be involved in the patient's care. Occasionally, though, if staffing is limited or there is high clinical acuity in the subject's case (e.g. massive postpartum hemorrhage), the anesthesiologist co-investigator who consented the patient may need to be involved in helping with the patient's intraoperative care. If this is the case, coercion will be avoided since the patient consent will occur first, and the study investigator will only become the patient's physician after the informed consenting process is complete. Patients, obstetricians, study co-investigators and nurses will be blinded to the study group assignment but the anesthesiologist will be unblinded to study randomization and the identity of each drug being given.

At the time of administration of the first study drug, the anesthesiologist will ask the obstetrician to rate the uterine tone on a scale of 0 to 10 (0 being 'no tone', 10 being 'excellent tone'). The anesthesiologist will then set a timer. After administration of the study drug, patients will receive our usual standard of care. At 5 minutes and again at 10 minutes from the onset of timing, the anesthesiologist will once again ask the obstetrician for a rating of uterine tone between 0 and 10. These values will be recorded by the anesthesiologist on the Uterine Tone Score Intraop Data Collection sheet provided in the envelope with the Randomization sheet by the investigator.

If a third uterotonic is desired (after oxytocin and the initial study drug), the patient will receive the alternate drug (methylergonovine or carboprost), prepared by the unblinded anesthesiologist. Any additional measures for postpartum bleeding will be provided in the usual fashion as standard of care.

At the end of the C/S, the anesthesiologist will return the Randomization sheet and the Uterine Tone Score Intraop Data Collection sheet in the previously sealed envelope to a folder where all paper documents for the study are temporarily stored in a locked room on the L&D floor. On each day of subject enrollment, the unblinded principal investigator will collect the envelope with the Randomization sheet and Uterine Tone Score Intraop Data Collection sheet and transfer it to a locked filing cabinet in a locked office to which only the principal investigator has access.

After the subject has recovered on the L&D floor and is ready for transfer to the postpartum floor, a blinded study co-investigator will interview the patient by phone (to limit physical contact, due to COVID-19 precautions)

using the '2-4 Hour Interview Guide'. At 18-24 hours postpartum, the subject will again be interviewed by phone by a blinded study co-investigator, using the '18-24 Hour Interview Guide'. Both postpartum interview guides will contain the same content, allowing for subjective adverse effects to be accurately assessed at 2 timepoints. (no later than 24 hours after delivery). This data will be documented on the 2-4 Hour and 18-24 Hour Interview Guides, to be retrieved by the principal investigator (who is not blinded) after the day of subject enrollment, then stored in the locked office, and ultimately entered into a secure electronic database, REDCap, by a blinded study investigator. This will allow them to assess for any subjective side effects of the study medication, as listed below (Secondary Endpoint #9).

An unblinded study investigator not involved in data collection and with access to REDCap will be responsible for collecting all primary and secondary outcomes (including side-effects of study medications) from the Uterine Tone Score Intraop Data Collection sheet, the Pre Transfer Interview Guide and Epic medical records onto the Second Line Uterotonics Data Collection Sheet and entering this information into REDCap. Subject randomization, patient MRN and the linked study ID number will be documented on a separate form in the REDCap database by the unblinded principal investigator, to preserve the integrity of the data collection and entry.

Study endpoints will be:

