The obstetrician and nurse, involved in the cases as well as the study investigator will be blinded to the study group assignments. All physician co-investigators (with the exception of the principal investigator) and the statistician will be blinded to study group assignments throughout the study. As such, these co-investigators will not be involved in the obstetric care of the study subjects, with the following one exception: Every effort will be made to keep the study investigator who consented the subject out of the operating room and uninformed in the subject's clinical care in all cases. However occasionally, due to staffing challenges and clinical acuity of a patient's case (e.g. massive hemorrhage), the anesthesiology attending or fellow who consented the patient may need to be involved in the patient's intraoperative or postoperative care. To minimize any chance of patient coercion and bias in clinical decision-making, the consent process will occur first with the study investigator anesthesiologist. Only after consent is complete and the patient enrolled will the same anesthesiologist who consented the patient end up caring for the patient. This scenario will only occur in situations when a staffing shortage occurs or the case requires additional help due to a life-threatening situation. Everything possible will be done to avoid that situation. Thus the patient will agree to participate in the study in advance of forming any physician-patient relationship with the study investigator, and the study investigator will only affect clinical care as a helper in case of clinical necessity, not as the leader of clinical decision-making (i.e. the study investigator will not be the primary anesthesiologist of record for the case).

The study drug will consist of either:

1. 0.2mg methylergonovine, or
2. 0.25mg 15-methyl prostaglandin F2a

The anesthesiologist will administer the study medication in a 1mL syringe intramuscularly in the patient's deltoid muscle. Each patient will have both medications available in the fridge where hemorrhage medications are stored, so that the second of the 2 drugs can be easily administered in succession if an additional agent is needed.

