Within the first 24 hours after delivery, but no sooner than the time of patient transfer from the labor and delivery floor to the postpartum unit, Between 2-4 hours postpartum and again between 18-24 hours postpartum, a blinded study investigator who is not involved in the subject's clinical care will interview the patient by phone (to avoid physical contact and minimize the risk for COVID-10 transmission) and record the information from the interview on the corresponding '2-4 Hr Interview Guide' or '18-24 Hr Interview Guide'. This will allow them to assess subjective side effects of the study medication such as G.I. upset, dizziness, shortness of breath, palpitations or chest pain. Non-English speaking patients will be interviewed in person with the assistance of an in-person interpreter from BWH Interpreter Services.

Subject randomization, patient MRN and the linked study ID number will be documented on a separate form in the secure electronic database, REDCap database by the unblinded principal investigator. This form will be visible only to the principal investigator. An unblinded study investigator (i.e. the principal investigator, or a research assistant, when one is hired in the future) with access to REDCap will be responsible for collecting and entering all primary and secondary outcomes from the Uterine Tone Score Intraop Data Collection sheet, the 2-4 Hour Interview Guide and the 18-24 Hour Interview Guide and Epic medical records (including side-effects of study medications) into REDCap. Subject randomization will be documented, on a separate form in the database to which only the principal investigator has access, in order to preserve the integrity of the data collection and entry.

The need for blood product administration and quantity of each component given within 24hrs after cesarean section will be recorded. In addition, the investigator will record any additional interventions performed to halt bleeding, such as Bakri balloon placement, B-Lynch sutures, uterine artery embolization or hysterectomy.

Total intravenous fluids given from start to conclusion of the delivery will be recorded. The use of vasopressors, uterotonic agents, anti-emetic agents will be recorded. Length of stay and any postoperative complications occurring during the hospital stay will be documented at the time of hospital discharge.

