## **PRIVACY AND CONFIDENTIALITY**

Describe methods used to protect the privacy of subjects and maintain confidentiality of data collected. This typically includes such practices as substituting codes for names and/or medical record numbers; removing face sheets or other identifiers from completed surveys/questionnaires; proper disposal of printed computer data; limited access to study data; use of password-protected computer databases; training for research staff on the importance of confidentiality of data, and storing research records in a secure location.

NOTE: Additional measures, such as obtaining a Certificate of Confidentiality, should be considered and are strongly encouraged when the research involves the collection of sensitive data, such as sexual, criminal or illegal behaviors.

All data related to this study will be treated as confidential. Email communication to potential subjects at term gestation will be sent securely, in accordance with MGB Information Security guidelines. Collected data will be consolidated and entered directly in a de-identified fashion into a secure electronic capture tool, REDCap. Patient MRNs will be the only patient identifier recorded in REDCap; these will be entered with study group allocation and study ID number separately from the other study data into a secure document on REDCap by the unblinded principal investigator. The MRNs will be linked to study information on the randomization sheets, which will be viewed only by the unblinded principal investigator and stored in a locked filing cabinet in a locked office, accessible only by the principal investigator. Any other paper documentation related to study patients and containing patient identifiers will be maintained in the same locked filing cabinet, accessible only by the principal investigator.

Only the principal investigator, and one unblinded co-investigator will have access to the REDCap files. No one other than the study investigators will have any knowledge of the details of the patient's study information, and this data will never be circulated electronically or in any other format.

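### An unblinded investigator is assigned to collect and enter every outcome, which conflicts with other statements on blinding and database access; the plausible bias is confined to a few chart-judged secondary outcomes

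*Protocol*

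**What the plan says.** Two places give outcome handling to an unblinded person.

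- Protocol Summary, Research Design and Methods: "An unblinded study investigator not involved in data collection and with access to REDCap will be responsible for collecting all primary and secondary outcomes". The sources listed are the tone sheet, an interview guide and Epic, and the same person enters the data in REDCap.
- Detailed Protocol, section V, identifies the person as "An unblinded study investigator (i.e. the principal investigator, or a research assistant, when one is hired in the future". That person, "with access to REDCap will be responsible for collecting and entering all primary and secondary outcomes", works from the tone sheet, both interview guides and Epic.

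Four places say something different.

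- Protocol Summary, in the paragraph just before the sentence above: interview data are to be "entered into a secure electronic database, REDCap, by a blinded study investigator".
- Protocol Summary, Privacy and Confidentiality: "Only the principal investigator, and one unblinded co-investigator will have access to the REDCap files".
- Detailed Protocol, section V, on blinding: "All physician co-investigators (with the exception of the principal investigator) and the statistician will be blinded to study group assignments throughout the study".
- Protocol Summary, Research Design and Methods: the list of blinded parties includes study co-investigators, with no restriction to physicians.

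Section V also records allocation on a separate REDCap form that only the principal investigator can see. The stated reason is to protect the integrity of data collection and entry.

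**The concern.** The separate allocation form is meant to keep those who handle outcomes from knowing the drug. That purpose fails if the one person who can open the form also collects and enters the outcomes. The route to bias is detection bias: someone who knows the drug decides from the chart whether a patient had a complication. The conflicting role statements add a reporting problem, because a reader cannot tell from the plan which outcomes were handled blinded and by whom.

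**Working it through.** The plan gives no figure for this point, so the check is a comparison of texts.

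1. **Entry of interview data.** The Protocol Summary has a blinded investigator do it. Section V has the unblinded person enter data from both guides. The Privacy section gives REDCap access to two people only, both unblinded. Under that access rule, nobody blinded can enter anything.

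2. **Who the second unblinded person is.** Section V names a possible research assistant; the Privacy section names a co-investigator. The Summary's unqualified blinding of co-investigators contradicts the latter. Section V's statement covers physician co-investigators, so it is contradicted only if that co-investigator is a physician.

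3. **A narrower reading of the access rule.** The Privacy sentence might mean only the document that links MRN and allocation. It would then clash with section V, where that form is visible to the principal investigator alone. A conflict remains on either reading.

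4. **Where allocation can be seen.** The drug is charted openly in Epic (Agent Dispensing sections of the IRB application; section V). The tone sheet goes back in the same envelope as the Randomization Sheet. The tone sheet and interview guides do not themselves name the drug.

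5. **Outcomes with little exposure.**
   - Uterine tone is rated by a blinded obstetrician (section I) and arrives as numbers on a sheet.
   - Symptoms are elicited by blinded interviewers and recorded as yes or no.
   - Blood loss, hematocrit, transfused units, vasopressor use, ICU admission and length of stay are recorded facts.
   - Ischemic ECG change is a yes/no item on the intraoperative sheet, which the unblinded anesthesiologist completes. Who enters it later makes no difference.

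6. **Outcomes with real exposure.**
   - Hypovolemic shock has only a short working description on the data collection sheet (blood loss with signs of poor organ perfusion).
   - Acute renal dysfunction has no stated threshold in section II or in either endpoint list.
   - Transfusion-related lung injury or overload needs attribution.
   - Allergic reaction to transfusion needs attribution too, but the documents do not say whether the abstractor or the treating clinician makes it.

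7. **Scale of one decision.** With the planned 50 per group, one reclassified patient moves that arm's rate by 1/50 = 2 percentage points, and two move it by 2/50 = 4. The count is assumed. The documents give no basis for a number or a direction, so this is not an estimate of bias.

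8. **Who is available.** Blinded co-investigators already conduct both interviews. They could enter the guides, and the tone sheets too once those are separated from the Randomization Sheet. They could not abstract from an unmasked chart and stay blinded; the interview guides already tell them not to open the record before the form is complete.

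**The case against.** The best defense is that this is loose drafting with little consequence. The primary outcome is rated blinded, symptoms are elicited blinded, the statistician is blinded, and the allocation form is already hidden from everyone but the principal investigator. All of that stands, and it is why the point is limited to a few secondary outcomes.

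Several stronger readings are tempting, but the documents do not support them.

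- *The primary result is at risk from unblinded entry.* Copying three scores from a source sheet takes no judgement and can be verified. The anesthesiologist who writes the scores down is unblinded by design, and changing the data-entry staff would not alter that.
- *The Protocol Summary sentence contradicts itself.* It may mean a person who does not rate or interview patients but abstracts onto the collection sheet. It is badly worded, but not necessarily inconsistent.
- *The trial hides its unblinded roles.* The Summary calls the trial double-blinded, but both documents state openly that the anesthesiologist, the principal investigator and the person entering data know the allocation.
- *Blinded staff could take over all abstraction.* Epic shows the drug, so somebody unblinded must abstract the objective items and prepare any masked extract.

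What the defense does not answer is that the access rule excludes the blinded entry promised elsewhere, and that nothing in the plan provides blinded classification of the outcomes in step 6.

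**Conclusion.** The role and access statements conflict and should be reconciled. As section V stands, the person who alone sees the allocation form may also collect and enter every outcome, which defeats the plan's own safeguard. The threat to the primary outcome is small. Detection bias is plausible for hypovolemic shock, acute renal dysfunction and transfusion lung injury or overload, and for transfusion reaction if the abstractor makes the attribution. Neither its size nor its direction can be estimated from the documents.

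This rests on two assumptions: that the abstractor, not the treating clinician, decides at least some of these events, and that the chart is read unmasked. The plan states neither outright, but both follow from outcomes being collected from an openly charted record with no blinded review. The point is a worthwhile, inexpensive improvement, not a defect that undermines the trial.

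**What to change.** 1. Replace the conflicting text in section V (blinding and data entry) and in the Protocol Summary (Research Design and Methods; Privacy and Confidentiality) with one table of roles, blinding status and REDCap rights.
2. Have the existing blinded co-investigators enter the tone sheets and both interview guides, with REDCap rights that exclude the allocation form. Put the Randomization Sheet in its own sealed sleeve, and let the tone sheet reach them without it.
3. Leave the objective Epic items with the unblinded abstractor: blood loss, hematocrit, transfusion, vasopressors, ICU admission and length of stay.
4. Have that abstractor prepare an extract with uterotonic entries removed for every patient who meets an objective screen written in advance. A blinded co-investigator then classifies the outcomes in step 6 of the working from the extract, against written definitions.
5. The SAP is written in the past tense and reports 3 patients with missing tone, so entry may be complete. In that case, reclassify those events blinded from masked extracts, and report who entered what and whether they were blinded.

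The cost is a REDCap user-rights setting, one sleeve per envelope, revised wording and a short masked extract for a few patients. No new staff are needed. The screening step stays unblinded, so the route to bias is narrowed but not closed.
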